Fentanyl is a pure opioid agonist whose principal therapeutic action is analgesia. Other members of the class known as opioid agonists include substances such as morphine, oxycodone, hydromorphone, codeine, and hydrocodone.

Pharmacokinetics

Absorption:

In a study that compared the relative bioavailability of Lazanda and an oral transmucosal fentanyl citrate product, the bioavailability of fentanyl from Lazanda was approximately 20% higher. Fentanyl is absorbed from the nasal mucosa following intranasal administration of Lazanda, with median Tmax values ranging from 15-21 min after administration of a single dose. Cmax and AUC values for fentanyl following administration of Lazanda increase linearly over the 100- to 800-mcg dose range.

Distribution:

Fentanyl is highly lipophilic. The plasma protein binding of fentanyl is 80% to 85%. The main binding protein is alpha-1-acid glycoprotein, but both albumin and lipoproteins contribute to some extent. The mean volume of distribution at steady state (Vss) was 4 L/kg.

Metabolism:

The metabolic pathways following intranasal administration of Lazanda have not been characterized in clinical studies. The progressive decline of fentanyl plasma concentrations results from the uptake of fentanyl in the tissues and biotransformation in the liver. Fentanyl is metabolized in the liver and in the intestinal mucosa to norfentanyl by cytochrome P450 3A4 isoform. In animal studies, norfentanyl was not found to be pharmacologically active.

Elimination:

The disposition of fentanyl following intranasal administration of Lazanda has not been characterized in a mass balance study. Fentanyl is primarily (more than 90%) eliminated by biotransformation to N-dealkylated and hydroxylated inactive metabolites. Less than 7% of the administered dose is excreted unchanged in the urine, and only about 1% is excreted unchanged in the feces. The metabolites are mainly excreted in the urine, while fecal excretion is less important. The total plasma clearance of fentanyl following intravenous administration is approximately 42 L/h.

Adverse Reactions

Clinical Studies Experience

Because clinical trials are conducted under widely varying conditions, adverse event rates observed in the clinical trials of a drug product cannot be directly compared to rates in the

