The following baseline evaluations will be performed on consented subjects prior to study drug administration: vital signs, oxygen saturation, Ramsay Sedation Scale (Table 2) (Ramsay, 197). The baseline pain intensity will be rated using NRS, and a blood sample will be drawn for standard of care laboratory investigation of the cause of pain or exacerbation of pain.

Intervention:

Intervention Arm: A Lazanda dose [100 mcg] at time 0 (defined as the time when intranasal Lazanda spray is administered) with a rescue dose allowed at time 0.5 hour (h).

Control Arm: An equipotent opioid dose [hydromorphone 1.5 mg pushed intravenously (IV)] at time 0 (defined as the time of completion of opioid IV push) with a rescue dose allowed at time 0.5 hour (h).

For subjects with pain NRS > 4 who desire additional analgesics at thirty minutes after Time 0 (i.e., Time 30 minutes), a second dose of medication will be administered as in the table above. Subjects with excessive sedation (Ramsay Sedation Scale < 4) will not receive analgesics at Time 30 minutes.

After another 90 minutes (i.e., Time 120 minutes), for patients with unrelieved pain (NRS >6 and Ramsay Sedation Scale <4), the patient may receive supplemental IV bolus doses of opioid as clinically indicated and ordered by the treating physician.

Table 2. **Ramsey Sedation Scale**

Wakeful State	Scale	Description
If Awake	Ramsay 1	Anxious, agitated, restless
	Ramsay 2	Cooperative, oriented, tranquil
	Ramsay 3	Responsive to commands only
If Asleep	Ramsay 4	Brisk response to light glabellar tap or loud auditory stimulus
	Ramsay 5	Sluggish response to light glabellar tap or loud auditory stimulus
	Ramsay 6	No response to light glabellar tap or loud auditory stimulus

10 Evaluation during Study

We will perform measurements described in this section for 4 hours after initiation of the drug intervention while the patient is in the ED. The average length of stay for patients presenting with severe pain to our ED is currently 9 hours.

Pain Measurements: Pain measurement by NRS will be obtained at the time of randomization, time of treatment initiation, and every 15 min from administration of the first dose of pain medication up to Time 120 min and then every 30 min from Time 120 min to Time 240 min. At 60 min after randomization, one additional NRS rating will be obtained.

Primary Outcome Measure:

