The primary outcome measure is the non-inferiority of fentanyl nasal spray versus IV opioids in the treatment-wise response starting from the time of drug delivery. The decrease in pain level between treatment initiation and one hour after will be compared between intranasal fentanyl and an analgesic equivalent dose of intravenous opioid.

Secondary outcome measures:

For secondary objective 1, we will compare the decrease in pain level between randomization and one hour after randomization between intranasal fentanyl and an analgesic equivalent dose of intravenous opioid.

For secondary objective 2, we will monitor the safety and side effects of fentanyl nasal spray and intravenous opioid. Safety evaluation will include vital signs, oxygen saturation and respiratory rate. Blood pressure, heart rate, oxygen saturation and respiratory rate will be monitored for abnormalities. Adverse reactions of nausea and vomiting and neuropsychiatric adverse effects will be monitored. Sedation will be measured by Richmond Agitation Sedation Scale (RASS). The side effects rating scale for dissociative anesthetics (SERSDA) will be assessed at the end of the study period.

For secondary objective 3, we will estimate the time from randomization to IV establishment in adults with cancer presenting to the ED with severe pain.

Exploratory measures:

Time to maximal pain relief and Summed Pain Intensity Difference (SPID) (Davies et al., 2011) will be derived using NRS data for the 4-hour period for additional exploratory analyses. Time to maximal pain relief is defined as the time duration from Time 0 to the first occurrence of the lowest NRS in a subject. Pain intensity difference (PID) at a time point is defined as the NRS at Time 0 minus the NRS at that time point. The PID over the 4-hour study period will be integrated as the SPID using the trapezoidal method to calculate the area under the curve.

11 Adverse Events Recording

11.1. Adverse Events Monitoring:

Adverse event monitoring and reporting will begin after patients receive the study drug or IV hydromorphone and will continue to be recorded through discharge from the study. Patients will be instructed to report all unusual events during the study. All adverse events and corresponding treatment will be recorded in the case report forms and summarized in the final clinical study report. Any ongoing adverse events will be followed up by phone if the patient is discharged

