from the hospital or by patient visit if the patient is hospitalized, within 24 hours after study completion.

Intranasal fentanyl is generally well tolerated with the most common side effects consisting of nausea, vomiting, headache, and sedation (side effects common to all opioids).

Unexpected Adverse Drug Event

All external adverse events/safety reports received from the sponsor will be submitted to the IRB through the Office of Protocol Research as described for the “External Adverse Event Report” located under section 1 of the OPR Forms Manual.

Adherence to MDA Policy and Procedure for Reporting of Serious Adverse Events.

This study will follow the MDA policy and procedures for reporting of adverse and serious adverse events. All adverse events and serious adverse events will be documented and available for review if desired. Criteria for reporting of events before routine review will be determined based on established institutional guidelines.

12 Criteria for Evaluation and Endpoint Determination

Measurements

NRS measures will be obtained at triage, randomization, time 0 (initiation of drug intervention) and every 15 minutes for 120 minutes and then every 30 minutes from time 2 to 4 hours, and at 60 min after randomization.

Vital signs, oxygen saturation and respiratory rate will be recorded at each time point of NRS measurement.

Adverse reactions of nausea and vomiting and neuropsychiatric adverse effects will be monitored.

Sedation will be measured by Richmond Agitation Sedation Scale (RASS) (Table 3) at Time 1 h (i.e., one hour after initiation of drug delivery). RASS is a scale used to grade the sedation or agitation level of a patient in a clinical setting (Sessler et al., 2002).

Table 3: Richmond Agitation Sedation Scale

Points	Classification	Description
4	Combative	Overtly combative or violent; immediate danger to staff
3	Very agitated	Pulls on or removes tube(s) or catheter(s) or has aggressive behavior toward staff
2	Agitated	Frequent nonpurposeful movement or patient–ventilator dyssynchrony
1	Restless	Anxious or apprehensive but movements not aggressive or vigorous
0	Alert and calm	
-1	Drowsy	Not fully alert, but has sustained (more than 10 seconds) awakening, with eye contact, to voice

-2	Light sedation	Briefly (less than 10 seconds) awakens with eye contact to voice
-3	Moderate sedation	Any movement (but no eye contact) to voice
-4	Deep sedation	No response to voice, but any movement to physical stimulation

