-5	Unarousable	No response to voice or physical stimulation

The side effects rating scale for dissociative anesthetics (SERSDA) (Table 4; Eide et al., 1994) will be assessed at time 4h.

Table 4. Side effects rating scale for dissociative anesthetics

	Severity Scale: 0, no change; 1, weak; 2, modest; 3, bothersome; 4, very bothersome
Side Effects	Severity
Fatigue	
Dizziness	
Headache	
Feeling of unreality	
Changes in hearing	
Changes in vision	
Mood change	
Generalized discomfort	
Hallucination	
SERSDA score =	Sum of the Severity Scores of the above side effects

Study Variables

PROCEDURE-WISE ANALGESIC EFFICACY: The change in pain level between randomization and one hour after randomization will be compared between the intranasal fentanyl arm and the intravenous opioid arm. The power calculations are based on this primary efficacy variable.

TREATMENT-WISE ANALGESIC EFFICACY: Starting from the time of initiation of drug administration, the change in pain level after one hour will be compared between intranasal fentanyl arm and intravenous opioid arm.

TOLERABILITY: Tolerability to common adverse effects such as nausea and vomiting will be monitored. Neuropsychiatric adverse effects will be assessed by RASS and SERSDA. RASS score will be obtained at Time 1 h. SERSDA will be assessed after the final pain rating.

SAFETY: Blood pressure, heart rate, oxygen saturation and respiratory rate and adverse reactions will be monitored. Reports of adverse events will be collected spontaneously and in response to nondirected questioning. Investigators will ask how long the adverse effect lasted and categorize these events by seriousness (mild, moderate, or severe) and relationship to treatment (not related, doubtful, possible, probably, or very likely).

EMERGENCY CARE PROCESS CHARACTERIZATION: The time to IV establishment of adults with cancer presenting to the ED with severe pain after randomization will be estimated. Patients in both arms will have IV access. This time can be estimated using all

the study participants. The time to IV establishment can also be compared between the 2 study arms to check for bias in work flow in this open label study.

13 Data and Protocol Management

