The secondary efficacy endpoint is the change in NRS pain scores from randomization to one hour after randomization, which will be summarized using mean, standard deviation, minimum, median and maximum values. A two-sample t-test will be used to assess group difference in pain score change. In addition, analysis of covariance will be used to determine whether significant differences exist between the nasal fentanyl and IV hydromorphone groups in pain intensity scores at one hour post randomization with treatment group (fentanyl vs. IV hydromorphone) and baseline pain intensity included as independent variables. Models will be constructed to adjust for relevant baseline demographic and clinical factors, such as age, treatment dose, and disease type. Additional exploratory analyses will include time to maximal pain relief as well as summed pain intensity ratings for the entire observation period calculated as the sum of time-weighted pain intensity scores. Group differences in the summed pain intensity will be assessed using the area under the curve derived using the trapezoidal rule (Cappelleri et al., 2009).

Because study treatments are FDA approved for treatment of breakthrough pain in cancer patients, no formal safety monitoring rule will be established; however, all side effects and adverse events will be monitored continuously by the principle investigator. To address the secondary objective #2, the safety analysis will include data summaries of treatment side effects and adverse events by study group. Side effects will be tallied and reported by number and percent for the worst reported severity. Laboratory values and clinical measures will be summarized by treatment group using simple descriptive statistics, such as mean change from baseline value to the 4 hours after treatment initiation or end of treatment, whichever occurs first. In addition, any delayed side effects that occur during the first 24 hours will be reported. This randomized trial will be monitored by the MD Anderson Data Safety Monitoring Board.

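### RASS, the named sedation measure, is read once, at 60 min, with no RASS baseline, so change on the scale cannot be computed and sedation at other times may be missed.

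*Combined protocol and SAP*

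**What the plan says.** All references are to the combined protocol and SAP.

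- **Outcome scale.** Section 10, under the secondary outcome measures, names RASS for the safety objective: "Sedation will be measured by Richmond Agitation Sedation Scale (RASS".
- **Outcome timing.** Section 12 (Measurements) says "Sedation will be measured by Richmond Agitation Sedation Scale (RASS) (Table 3) at Time 1 h", and Study Variables in the same section repeats it: "RASS score will be obtained at Time 1 h". No other RASS reading is scheduled.
- **Baseline scale.** Section 7 (Baseline Measures) lists what is done "prior to study drug administration: vital signs, oxygen saturation, Ramsay Sedation Scale (Table 2". RASS is not on that list.
- **Other sedation checks.** Section 7 (Intervention) uses Ramsay at 30 min and at 120 min, in both places as a condition for giving further analgesic.
- **Contacts.** Section 12 has vital signs, oxygen saturation and respiratory rate taken whenever pain is rated. Sedation is not part of that schedule.
- **Pharmacokinetics.** Section 4 gives, for the spray, "median Tmax values ranging from 15-21 min after administration of a single dose". It gives no time to peak for IV hydromorphone.
- **Analysis.** Section 15 names no RASS analysis. For clinical measures it offers average change from the starting value as an example of a descriptive summary. For side effects it says "Side effects will be tallied and reported by number and percent for the worst reported severity".

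**The concern.** Section 11 lists sedation among the common side effects of the spray and of opioids in general. A non-inferiority claim on pain needs a credible comparison of harm beside it. One reading in a four-hour observation period gives neither a course over time nor a lowest value. Because the baseline is on another scale, it gives no change either.

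Baseline is relevant because section 5 admits only patients who have already taken daily opioids for at least a week, so some may be drowsy on arrival. With 42 patients per arm, a chance imbalance in drowsiness at entry could not be adjusted for on the outcome's own scale.

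The phase at which the single reading falls also depends on whether a second dose was given. That is decided after randomization and may differ by arm.

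**Working it through.** The plan states no figure for this point, so there is none to reproduce. The check is a comparison of the scales, some timing arithmetic, and a search for other data that could fill the gap.

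**1. Can change be computed?** Ramsay (Table 2) runs from 1 to 6, and higher means more sedated. RASS (Table 3) runs from +4 to -5, and lower means more sedated. The documents give no mapping between them. Ramsay at baseline and RASS at 60 min cannot be subtracted, so no change on RASS exists for any patient.

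**2. Where does the reading fall against the spray's plasma peak?** Inputs: median Tmax 15 to 21 min (section 4), first dose at 0 min, second dose allowed at 30 min (section 7), RASS at 60 min (section 12). Gap = 60 - (dose time + Tmax).

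| Dose | Plasma peak | Gap to the RASS reading |
|---|---|---|
| First, 0 min | 15 to 21 min | 60 - 21 = 39 to 60 - 15 = 45 min |
| Second, 30 min | 30 + 15 = 45 to 30 + 21 = 51 min | 60 - 51 = 9 to 60 - 45 = 15 min |

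The second row assumes that the single-dose Tmax also holds for a second dose. The documents do not say what share of patients will take one. No such table can be made for hydromorphone. Supplemental IV opioid, possible from 120 min, has no RASS reading after it.

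**3. How many contacts carry a sedation score?** Pain and vital signs are taken every 15 min from 0 to 120 min (9 points), then at 150, 180, 210 and 240 min (4 points): 9 + 4 = 13 contacts. RASS is taken at 1 of the 13.

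**4. Do other data fill the gap?**

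- *Ramsay at 30 and 120 min.* These are dosing conditions. They are absent from the section 12 measurement list and have no stated analysis. As written, they matter for patients who want a second dose, or whose pain is still above 6 at 120 min, so a recorded value for all 84 patients is not assured.
- *SERSDA.* It is taken once, at 4 h. None of its nine items is sedation; the nearest is fatigue.
- *Adverse events.* Section 12 collects them from spontaneous reports and open questions. A drowsy patient is poorly placed to report drowsiness, and the study is open label.

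None of the three is a systematic sedation series in both arms.

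**The case against.** The strongest reply is that the consequences are easily overstated. A reader might infer four things that the documents do not support.

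- **That peak sedation is missed, or that sedation will be under-counted.** Section 4 gives a plasma Tmax, not a sedation peak, and no sedation time course is given for either drug. The 39 to 45 min gap measures from the latest peak only in patients without a second dose. Patients enter with pain of 7 or more and may ask for a second dose when pain is above 4. For those who receive one, the gap may be only 9 to 15 min. What can be said is that sedation may be missed, possibly unequally by arm.
- **That the arm comparison is biased without a baseline.** It is not. Randomization makes a comparison of 60-min RASS valid.
- **That the plan contradicts its own worst-severity report.** That sentence in section 15 concerns tallied side effects and does not mention RASS. It fits the graded adverse events and SERSDA items. Nor does section 15 promise a RASS change score; change is only its example of a summary.
- **That sedation is observed only once.** Ramsay is taken at baseline and used at two later times, and sedation can be reported as an adverse event.

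It is also fair that 60 min matches the primary endpoint. Marked drowsiness at entry is limited too, because patients must be able to consent and to rate their pain repeatedly, and recent oral immediate-release opioid use is excluded.

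All of this stands. It limits the claim but does not supply a same-scale baseline, a time course, or a lowest value from more than one reading.

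**Conclusion.** The point holds in a limited form. The named sedation measure is read at 1 of 13 scheduled contacts and has no baseline on its own scale. Change on RASS cannot be computed, a worst RASS would be the single 60-min value, and sedation at other times is not systematically captured as outcome data. The documents do not allow the amount of missed sedation, or any difference by arm, to be estimated.

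The first-dose gap of 39 to 45 min rests on the protocol's median Tmax. The second-dose gap of 9 to 15 min further assumes dosing at exactly 30 min and an unchanged Tmax. Neither gap locates peak sedation.

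What is lost is baseline adjustment, individual change and the course over time, within a descriptive part of secondary objective 2. The primary non-inferiority conclusion is unaffected. The change is worth making because it is cheap and improves what the safety objective can conclude.

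**What to change.** **Measurement.** Record RASS immediately before study drug and at each scheduled pain and vital-sign contact from 15 to 120 min. That is 1 + 8 = 9 readings, of which the 60-min one is already planned, so 8 are added per patient. The minimum version adds only the pre-dose reading; it allows change to be computed but gives no time course. Readings to 120 min would still not show sedation after supplemental opioid given from that time. The four contacts from 150 to 240 min could be added if the team wants that period covered.

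**Analysis.** State in section 15 that the following will be reported by arm: the lowest RASS, the change from the pre-dose value, and the number of patients at or below a RASS level fixed before the data are seen. Keep the 60-min comparison.

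**Cost.** A brief bedside rating at contacts where vital signs are already taken, so slight extra nurse time, plus one case-report-form line per contact.

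This changes no dosing rule. Separately, section 7 (Intervention) says "Subjects with excessive sedation (Ramsay Sedation Scale < 4) will not receive analgesics at Time 30 minutes", yet makes the same Ramsay range a condition for supplemental opioid at 120 min, while Table 2 places the asleep states at 4 to 6. These passages contradict each other and must be reconciled by the study team.

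### Nausea and vomiting are to be monitored but have no scale, fixed question or baseline rating; the only stated elicitation rule is nondirected, so the by-arm summary is likely to undercount nausea and capture could differ by arm.

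*Combined protocol and SAP*

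**What the plan says.** Nausea and vomiting appear repeatedly as effects of interest. Section 11.1 describes intranasal fentanyl as generally well tolerated, with "the most common side effects consisting of nausea, vomiting, headache, and sedation". Sections 10 and 12 both state: "Adverse reactions of nausea and vomiting and neuropsychiatric adverse effects will be monitored". The Tolerability paragraph of Section 12 (Study Variables) says: "Tolerability to common adverse effects such as nausea and vomiting will be monitored".

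Two rating scales are specified, and the same paragraph gives their purpose: "Neuropsychiatric adverse effects will be assessed by RASS and SERSDA". RASS is taken once, at 1 hour. SERSDA is taken at 4 hours, and its total is defined in Table 4 as the "Sum of the Severity Scores of the above side effects", of which there are nine.

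The Safety paragraph of Section 12 gives the elicitation rule: "Reports of adverse events will be collected spontaneously and in response to nondirected questioning". Section 11.1 adds: "Patients will be instructed to report all unusual events during the study". Adverse event recording starts only after dosing. Section 12 describes the study as open label. In Section 15 the safety analysis is a descriptive summary by study group: "Side effects will be tallied and reported by number and percent for the worst reported severity".

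**The concern.** Section 11.1 names four common effects. Sedation has an instrument (RASS) and headache has a SERSDA item. Nausea and vomiting have neither, so for these two the by-arm tally depends on what patients volunteer or mention in reply to an open question. The mild, moderate or severe grade in Section 12 applies only once an event has been reported, so a symptom nobody mentions never reaches the worst-severity table.

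Two features add to this. Every participant has been on opioids for at least a week at a set minimum dose (inclusion criterion 1), and Section 11.1 calls these effects common to all opioids. Being asked for unusual events may not prompt such patients to mention nausea. Both patients and staff also know the allocation, so without fixed wording the depth of questioning can vary by arm.

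At stake is the reading of secondary objective 2. A difference in nausea between arms could come partly from how it was asked about, and a real difference could be shrunk.

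**Working it through.** **1. Coverage, by comparing sections**

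- RASS (Table 3) grades agitation and sedation only.
- SERSDA (Table 4) has nine items: fatigue, dizziness, headache, unreality, hearing, vision, mood, generalized discomfort and hallucination. None is nausea or vomiting.
- Baseline Measures (Section 7) comprise oxygen saturation, vital signs, the Ramsay score, the NRS and a blood sample. No nausea rating is listed.
- The monitoring statements in Sections 10 and 12 give no question, scale or time point for nausea or vomiting.
- Those statements call nausea and vomiting adverse reactions or adverse effects. The adverse event rule in the Safety paragraph is therefore the only stated elicitation method that reaches them.

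**2. What is not affected**

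The sample size uses no nausea input. The plan gives no SD for the non-inferiority endpoint. Assuming the pooled SD from its two stated SDs, √((1.86² + 1.40²)/2) = 1.646, and with margin 0.9, one-sided 0.05 and 80% power:

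n per arm = 2 × (1.645 + 0.842)² × 1.646² / 0.9² ≈ 41.4, rounded up to 42.

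This reproduces the plan's 84 patients.

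**3. Illustration of size**

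Only the 42 per arm comes from the documents. The true nausea rate p and the capture probability c are assumptions.

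Expected recorded cases = 42 × p × c. False gap with equal true rates = p × (c₁ − c₂).

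| True rate, both arms | True cases per arm | Recorded, 50% capture in both | Recorded, 80% vs 50% | False gap |
|---|---|---|---|---|
| 20% | 8.4 | 4.2 | 6.7 vs 4.2 | 6 points |
| 30% | 12.6 | 6.3 | 10.1 vs 6.3 | 9 points |
| 40% | 16.8 | 8.4 | 13.4 vs 8.4 | 12 points |

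A milder split of 60% vs 40% at a true 20% gives 0.20 × 0.20 = 4 points. A wider one of 80% vs 40% at a true 40% gives 0.40 × 0.40 = 16 points.

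Equal undercapture creates no false gap but shrinks a real one. A true 40% vs 20% with 50% capture in both arms is recorded as 20% vs 10%, so 20 points become 10.

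**4. Compared with chance variation**

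With perfect capture, the 95% half-width for an arm difference is 1.96 × √(2p(1 − p)/42). That is 17 points at p = 20% and 21 points at p = 40%.

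**The case against.** The strongest reply is that the method for nausea and vomiting is unspecified, not specified as unprompted. The nondirected rule is in the Safety paragraph and concerns adverse events in general. Nausea and vomiting are in the Tolerability paragraph and have their own line under Measurements, which could mean targeted monitoring. This stands as far as it goes: a reader might infer that the plan says these symptoms are collected by nondirected questions, and it does not say so. But no other method is written anywhere. If direct questioning is intended, the remedy is still to write it down.

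Second, a reader might infer that undercounting is certain. The documents do not support that. Vomiting is visible, and staff contact follows the same dense NRS schedule in both arms. Treatment given for adverse events is recorded, the investigator monitors side effects continuously, and delayed effects in the first 24 hours are reported. These routes reduce the loss, mainly for vomiting. Equal contact is not equal questioning, however, and nausea is not visible.

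Third, nausea present on arrival is not impossible to separate from later nausea. Investigators ask about duration and classify relatedness, and history is reviewed at screening. A pre-dose rating would make the separation systematic and independent of unblinded judgement.

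Fourth, the two scales are assigned to neuropsychiatric effects and cannot be faulted for omitting nausea. That is right. The gap lies in the overall assessment plan, not in the instruments.

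**Conclusion.** The point holds as a likely weakness of ascertainment for nausea, less so for vomiting, in an open-label comparison. Differential capture by arm is possible but not shown; nothing in the documents indicates that either arm would be questioned less closely.

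Its size is unknown. The 4 to 16 point range rests wholly on assumed rates and capture probabilities. It should not be read as an expected bias, and all of it lies below the sampling uncertainty at 42 per arm. Bias does not average out as sampling error does, so that limits the practical consequence without removing the problem.

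A reader might also infer that the trial's safety conclusion or its main result is compromised. Neither follows. Secondary objective 2 is to monitor safety, its analysis is descriptive with no planned test, and the primary non-inferiority test and sample size do not use these data. This is an inexpensive improvement worth making, not an error that invalidates the plan.

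**What to change.** Keep nondirected questioning for all other events. For these two symptoms:

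- Add one nausea item and one vomiting item, read with identical wording in both arms. Ask them before the drug, and again at a few existing NRS times, for example 30, 60 and 120 minutes. Time 0 in the control arm is the end of the IV push, so tie the first rating to the pre-dose baseline measures.
- Score both on an absolute scale: 0 = none, then mild, moderate, severe. This matches the adverse event grades in Section 12. The SERSDA 0-4 scale is unsuitable because its zero means no change, so a pre-dose score would have no reference point.
- In Section 15, report by arm the worst post-dose severity and the number and percent with new or worsened nausea or vomiting, separately from spontaneously reported events.
- In Section 11.1, replace the instruction about unusual events with *any new or worse symptom, including nausea and vomiting*.

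The cost is two short questions at contacts already made for NRS and vital signs (12 after dosing, plus baseline), a few case report form fields and some analysis wording. There are two limits. Solicited rates will be higher in both arms and less comparable with trials that used spontaneous reporting. Fixed wording also cannot stop patients' knowledge of their arm from affecting their answers.
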